This will be a randomized control trial to study the efficacy of a combined lidocaine and corticosteroid injection on pain, range of motion, and patient reported outcomes versus a corticosteroid injection alone for the treatment of common upper extremity tendinopathies and nerve entrapments that are often treated with a combination of these injectates. Patients will be assigned randomly to a control group (corticosteroid injection alone) or the treatment group (lidocaine plus corticosteroid injection). At the initial injection a 10-point likert scale prior to and after the injection will be administered. The patients will be followed up at 6 weeks after the injection, at which time the Visual Analog Scale for pain (VAS-pain), range of motion (ROM), and patient reported outcome data will be collected and any complications will be noted. Patients will also utilize a pain journal to track VAS-pain over the first 7 post-injection days. We hypothesize that those who receive lidocaine plus corticosteroid injection will be non-inferior in regards to pain, range of motion (ROM), failure of injection requiring surgery, and patient reported outcome scores compared with patients who received corticosteroid injection alone.

Background and Significance:

Tenosynovitis is a common ailment of the upper extremity resulting in pain around the affected joint due to injury to the tendon sheath. One of the most common manifestations of tenosynovitis is trigger finger. Trigger finger is an extremely common pathology encountered by primary care providers and hand surgeons. Reported incidence of 28 cases per 100,000 has been documented [1]. This entity occurs when the contents of the flexor tendon sheath do not fit cleanly

within the sheath, causing friction on movement of the fingers. Progression from a clicking or locking sensation to complete inability to flex or extend the finger (hence the designation “trigger finger”) occurs over the course of the disease. Therefore, triggering may not be initially noted on exam. Pain from this pathology can be experienced at the proximal interphalangeal joint, the metacarpophalangeal joint, or even the palm [2]. Reported increases in rates have been documented in diabetics, cases of repetitive trauma, those with renal and thyroid disease, and individuals with inflammatory conditions [3].

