In addition, similar pathologies exist where the role of lidocaine remains vague. One such pathology is de Quervain tenosynovitis. de Quervain tendinopathy affects the abductor pollicis longus (APL) and extensor pollicis brevis (EPB) tendons in the first extensor compartment at the styloid process of the radius. It is characterized by pain or tenderness at the radial side of the wrist. Although de Quervain tendinopathy is often attributed to overuse or repetitive movements of the wrist or thumb, the cause is generally unknown. It most commonly affects women between the ages of 30-50 years old [28].

A small randomized trial found that glucocorticoid injections resulted in significantly better symptom improvement compared with placebo one week after injection [29]. Among those who responded to glucocorticoid injections, the beneficial effects were maintained during the 12-month follow-up period. Another randomized trial also found that splinting plus glucocorticoid injection was better than splinting alone [30]. Most patients experience pain relief after a single glucocorticoid injection [30, 31]. In patients with recurrent symptoms after initial relief with the

first glucocorticoid injection, a second injection may provide benefit. However, limited evidence is available about the role of lidocaine during these injections. We further aim to elucidate the role of corticosteroid and lidocaine versus corticosteroid alone in the treatment of de Quervain tenosynovitis.

Furthermore, the role of lidocaine with corticosteroid in the treatment of a number of other tenosynovitides remains ambiguous. These include tenosynovitis of the shoulder, biceps, elbow, wrist, thumb, carpometacarpal, midcarpal, elbow, and small joints of the hand (PIP, DIP, MP). We aim to ascertain whether the corticosteroid and lidocaine injectate together is as effective as corticosteroid in the treatment of these tenosynovitides. For all these pathologies corticosteroid with or without lidocaine is standard of care for orthopaedic hand and shoulder surgeons and the use of either treatment regimen is based on personal preference by the surgeon.

Objectives:

1. Determine differences in pain scores / likert scale at the time of injection and during follow up in the corticosteroid plus lidocaine group as compared to the corticosteroid alone group.

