Patients in the Corticosteroid and Lidocaine group will be treated with a 40 mg/mL injection of corticosteroid combined with 1% lidocaine. The volume of injectate differs for each tenosynovitis being treated. For example, patients being treated for trigger finger will receive 0.5 mL of 1% lidocaine and 1 mL of 40mg/mL triamcinolone.

Needle size and insertion site of needle differs for each tenosynovitis being treated. For trigger finger specifically, needle injections will be performed with an appropriately sized needle inserted over the A1 pulley at a 45-degree angle. The injection will be done with the same technique for both groups by the attending physician. The medication will be injected extra-synovially in order to make the treatment more reproducible. This method of injection has been supported in previous studies.

Outcome Measures:

- Likert Scale: A 10-point likert scale will be asked before and after injection which has been previously validated in other studies looking at efficacy and pain surrounding injections of the upper extremity.
- Pain Assessment: A pain assessment will be assessed before performing the injection, at the time of injection, and at each subsequent follow up visit. Pain scores will be obtained via the Visual Analog Pain Scale (VAS-pain), which is ranked from 0 (no pain) to 10 (highest amount of pain). Pain will be assessed at rest and active movement of the affected joint. Patient will also be asked to fill out the VAS-pain score twice daily in a pain journal (once in the morning and once at night) each day until post-injection day 7.
- qDASH/PRWE/ASES/SF12/EQOL score: These scores will be administered at each clinic follow up. They will also be administered 6 week after the injectate has been performed.
- Need for subsequent reinjection and surgical operation will be recorded.

These scores, specifically the 10-point likert, will also be assessed before performing the injection, immediately after the injection, and again at the various follow up appointments. During clinic follow up we will monitor for complications.

Inclusion Criteria:

- All adult clinical patients of Emory upper extremity surgeons undergoing injection for treatment of the following who are willing to participate in the study will be included in the study: Tenosynovitis of the upper extremity, including but not limited to, the shoulder, biceps, elbow, wrist, thumb, carpometacarpal, midcarpal, elbow, and small joints of the hand (PIP, DIP, MP).

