- Between the ages of 18 years and 95 years.

- For trigger finger: patients with a diagnosis of stenosing tenosynovitis based on a history of triggering and the presence of tenderness over the A1 pulley upon clinical examination. All patients, based on the Quinnell grading of trigger finger see in the figure below, will be included.

Grade	Clinical findings (during flexion and extension)
0	Normal movement
I	Uneven movement
II	Actively correctable
III	Passively correctable
IV	Fixed deformity

Exclusion Criteria:

- Patients who are minors, vulnerable subjects, or who are not willing to consent to participate in the study.
- Allergies to glucocorticoids, current daily use of glucocorticoids or strong opioids (morphine, fentanyl, hydromorphone, ketobemidone, methadone, nicomorphine, oxycodone, and meperidine), severe diabetic neuropathy of the hand influencing pain perception, rheumatoid arthritis, and neurological or psychiatric diseases, potentially influencing pain perception.
- Subjects who, in the opinion of the investigator, may be non-compliant with study schedules or procedures.

Statistical Analysis:

Data will be stored on an excel spreadsheet. We will collect the name, medical record number, age at time of surgery, ethnicity, gender, BMI, presence of diabetes, Quinnell grading of trigger finger, smoking status, pre-injection VAS-pain, post-injection VAS-pain, 10 point likert scale, complications, and need for repeat injection or surgical release. It is possible that other variables may be added depending on analysis. Each variable will be used as a nominal variable when possible (e.g. smoking status) or a continuous variable if needed (e.g. VAS-pain, patient related outcome scores). For some statistical calculations we may break up the continuous variables in to ranges (e.g. Ages 15-20, 25-30). We will perform statistical analysis using unpaired, 2-tailed Student t test to compare means for normally distributed data, Kruskal-Wallis test to compare medians of non-normally distributed data, and chi-square test to compare proportions. Statistical significance will be interpreted as $P < .05$. Confidence intervals will be calculated with a confidence level of 95%.

Specifically, the 2 groups will be compared using the Mann-Whitney U test to analyze the difference between the post-injection VAS scores. The Wilcoxon sign-rank test will be used to test the difference between the treatment and control group for pain and patient related outcomes.

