The minimally clinically important difference (MCID) varies for each outcome measure. Therefore, for the purposes of a power analysis, we will use the VAS-pain at the time of injection as the primary outcome. A similar study was published in 2017 from Earp *et al.* comparing needle-free jet lidocaine for pre-corticosteroid injection anesthesia with simultaneous lidocaine and corticosteroid injection. Using the results of this study as a metric, for the purposes of our study, to determine a 1-point change in VAS (4.5 to 3.5) with the reported standard deviation of 2 (SEM

was 0.4, with 30 subjects in each group) in the Earp *et al.* study, the number needed to treat to detect a difference between the treatment and placebo group would be 63 [32]. Therefore, we aim for a sample size of 63 patients for each possible tenosynovitis described in the inclusion criteria.

In total, **we plan to enroll 1000 patients total into this study** when combining all possible tenosynovitides encountered at Emory. These outcomes will be feasible to obtain in a reasonable time frame given the high volume of patients treated for tenosynovitis of all types at Emory. Patients will be grouped together for analysis and also broken into subgroups for sub-analysis based on primary diagnosis for injection.

JMP Pro Software or SPSS will be used to analyze the data and perform the statistics.

Risks to participation

Risks to participation include breach of confidentiality from PHI used to conduct the study. Every effort will be used to scrub data when possible and to use subject numbers/unique identifiers when possible.

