As stated above, the first line treatment for trigger finger is corticosteroid injection with lidocaine, although there are a significant proportion of hand surgeons who inject corticosteroid alone. As no study has evaluated the efficacy of lidocaine mixed with the injectate versus corticosteroid alone, our study does not constitute deviation from current status quo of best medical practice for the treatment of trigger finger. **Both treatment options are considered standard of care and it is solely based on physician preference for which regimen is chosen as an injectate.** Patients will be notified of any potential risks with signed written consent as they would before any standard corticosteroid injection for the treatment of trigger finger. They will also be asked to sign an additional consent form agreeing to participate in our study outlining the nature of the study and the fact that no deviation from current best medical practice will occur throughout the course of the study.

Benefits to future subjects or science

By identifying whether or not lidocaine combined with corticosteroid injectate leads to improved patient outcomes as compared with corticosteroid injection alone, we will be able to educate physicians and patients on best medical practice for treatment of trigger finger. Additionally, as lidocaine has been reported to cause significant burning during injection, if there is no additional benefit to addition of lidocaine to corticosteroid injection, we will be able to spare future patients the discomfort of combining the injectate with lidocaine.

Data safety and monitoring plan:

Patients will be followed up closely in clinic at 2 weeks and 6 weeks post-injection to ensure patients did not experience side effects from the injection and to assess for efficacy of the injection. A low dose of corticosteroid and lidocaine is being utilized and we do not anticipate adverse effects.

Patients will have the ability to remove themselves from this study either completely or partially, and these options will be elucidated on the written consent form.

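### The VAS rating named as primary is not carried through the plan as one defined rating with one test

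*Combined protocol and SAP*

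**What the plan says.** A primary outcome is named once, in the sample-size paragraph of Statistical Analysis, and there only for the power calculation: "we will use the VAS-pain at the time of injection as the primary outcome". The other sections treat pain as follows.

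- **Statistical Analysis, data list and tests.** VAS appears as a pre-injection and a post-injection item. The Mann-Whitney U test is named "to analyze the difference between the post-injection VAS scores", with no time given. The next sentence assigns the Wilcoxon signed-rank test to the group comparison of pain and patient-reported outcomes. The general paragraph before it lists the t test and Kruskal-Wallis for continuous data and gives VAS as an example of a continuous variable.
- **Outcome Measures.** VAS is taken before the injection, at the injection and at each follow-up visit, and twice daily in a journal to day 7. "Pain will be assessed at rest and active movement of the affected joint". The closing paragraph singles out the Likert scale, which is to be taken immediately after the injection among other times.
- **Precis/Abstract.** "At the initial injection a 10-point likert scale prior to and after the injection will be administered". VAS is placed at 6 weeks and in the 7-day journal.
- **Objectives.** Objective 1 reads "Determine differences in pain scores / likert scale at the time of injection and during follow up", so it covers two instruments and two periods.
- **Expected effect of lidocaine.** Under Benefits to future subjects or science, "lidocaine has been reported to cause significant burning during injection". The Lay Summary says that it blocks pain, but only for a moment.

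**The concern.** A primary outcome needs an instrument, a moment, a condition and a test. The plan supplies the instrument and the visit and leaves the rest open. An analyst holding the final data set could report injection-visit VAS at rest or on movement, a rating of pain during the needle or one taken just after it, or the Likert score, and could defend each from some part of the text. No hierarchy or multiplicity rule decides between them.

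The choice matters more here than in most trials because lidocaine is the studied difference between the arms. By the plan's own account it may add pain while it goes in and remove pain shortly afterwards. The stated expectations do not settle the direction. The null-numbered hypothesis expects less pain with corticosteroid alone, the abstract expects the lidocaine arm to be non-inferior, and the sample-size paragraph does not say which arm has the mean of 3.5.

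**Working it through.** **1. The plan's own figure.** From the sample-size paragraph: difference 4.5 − 3.5 = 1 point, SD 2. From Statistical Analysis: alpha 0.05, two-sided. Power and allocation ratio are not stated; I assume 80% and 1:1.

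n per arm = 2 × (1.960 + 0.842)² × SD² / difference² = 2 × 7.849 × 4 / 1 = 62.8, rounded up to 63.

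The plan's 63 is reproduced as a per-arm number for one VAS variable. (It is written as a number per diagnosis; that is a separate matter and is not pursued here.)

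**2. Is that variable defined elsewhere?**

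| Element | What the plan fixes | What it leaves open |
|---|---|---|
| Instrument | VAS (sample size, Outcome Measures) | The abstract gives only the Likert at this visit; Objective 1 gives both |
| Moment | The injection visit | During the needle or just after it; whether the post-injection item is this rating |
| Condition | None | Rest or movement |
| Scale of analysis | None stated for the primary | Raw score or change |
| Test | Mann-Whitney for post-injection VAS | The signed-rank test is also assigned to pain; it is a paired test and does not suit two independent arms |

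**3. False-positive risk if the headline can be chosen.** If each of k candidates is tested at 0.05 with no true effect, and they are independent, the chance of at least one P < .05 is 1 − 0.95^k:

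- k = 2: 1 − 0.9025 = 9.8%
- k = 4: 1 − 0.8145 = 18.5%
- k = 6: 1 − 0.7351 = 26.5%

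For correlated candidates, one million draws of equicorrelated normal statistics give the share with max |Z| > 1.96:

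| Assumed correlation | k = 2 | k = 4 | k = 6 |
|---|---|---|---|
| 0 (formula) | 9.8% | 18.5% | 26.5% |
| 0.5 | 9.1% | 15.6% | 20.8% |
| 0.7 | 8.3% | 12.9% | 16.5% |
| 0.8 | 7.8% | 11.5% | 13.9% |

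Two candidates could be a during- and an after-injection VAS. Four could be VAS at injection, post-injection VAS at rest, the same on movement, and the Likert. Six would add the journal and the 6-week VAS.

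**4. Direction (illustration only).** At 63 per arm, SE = 2 × √(2/63) = 0.356.

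- If lidocaine adds 1 point during the needle, Z is centred at 1/0.356 = 2.81, and the chance of a significant result against lidocaine is Φ(2.81 − 1.96) = 80%.
- If it removes 1 point just afterwards, the chance of a significant result in its favour is also 80%, by symmetry.
- With half-point effects, 0.5/0.356 = 1.40, and each chance is Φ(1.40 − 1.96) = 29%.

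The documents give no size for either effect, so these values show only that the reading chosen could matter.

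**The case against.** The sponsor can fairly say that a primary is named, with one instrument and one visit, and that Outcome Measures schedules a VAS at that visit. Other sections list further outcomes without calling any of them primary, which is normal, and an abstract that omits a measurement is weaker than one that contradicts it. The post-injection item may simply be a loose label for the same rating, entered just after the needle. All of this stands, and it rules out several stronger readings that a reader might infer:

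- **That VAS is not scheduled at the injection.** Outcome Measures schedules it. Only the abstract omits it.
- **That post-injection VAS is a different time from the primary.** The text does not show this. The supportable statement is that its time is undefined.
- **That Mann-Whitney is the only test offered for VAS.** The signed-rank test is also assigned to pain, and general tests are listed for continuous data. This adds to the ambiguity.
- **That lidocaine's effect changes sign between during and after.** The burning is described as something reported, and the momentary block comes from a lay summary. Neither has a size or an onset time.

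The objection does not reach the remaining gap. The primary is named only for the power calculation, its moment and condition are never stated, and no test is called primary or linked to it.

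**Conclusion.** The point holds in a limited form. The plan names a primary outcome but does not tie it to one rating and one test, and the sections that should do so differ on instrument, condition and timing. This goes beyond missing detail because, on the plan's own description of lidocaine, the during and after readings could support different conclusions.

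The error rates in the working are what free choice among the candidates would allow. They depend on the assumed number of candidates and on equal correlation between them. They are not the trial's actual error rate: an analyst who kept to one prespecified rating would stay at 5%. It should be corrected, and correcting it is cheap.

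**What to change.** Before outcome data are examined:

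1. In the sample-size paragraph, state that the primary outcome of the trial, and not only of the power calculation, is one VAS rating at the injection visit. The sponsor fixes its moment (for example, pain felt during the injection, recorded once immediately afterwards), its condition if rest or movement is relevant, and whether the raw score or a change is analysed.
2. In the Statistical Analysis data list, add that rating if the post-injection VAS is not already it. Attach one between-group test to it; the Mann-Whitney U already named will serve. Remove the signed-rank test from the between-group comparison.
3. List every other VAS rating (rest, movement, journal, follow-up) and the Likert as secondary, and bring Objective 1 into line.
4. Add VAS at injection to the abstract. Outcome Measures needs only the moment and condition defined.
5. State one expected direction for the primary, so that the hypotheses, the abstract and the 4.5 and 3.5 means agree.

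If the 1-point difference and SD 2 apply to the chosen rating, 63 per arm under the assumptions above is unchanged. The cost is protocol wording and possibly one data field, which would have to be collected at the injection visit.

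### The sample-size inputs give 63 patients per arm, but the target is written as 63 patients per tenosynovitis; applied as written, a diagnosis subgroup would have about 50% power for the 1-point difference.

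*Combined protocol and SAP*

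**What the plan says.** The sample-size paragraphs of the Statistical Analysis section take VAS-pain at the time of injection as the primary outcome for the power analysis. They use a 1-point difference (4.5 to 3.5) and an SD of 2 drawn from a published trial, whose SEM, the plan notes, "was 0.4, with 30 subjects in each group". From these figures, "the number needed to treat to detect a difference between the treatment and placebo group would be 63". The next sentence turns that number into the target: "Therefore, we aim for a sample size of 63 patients for each possible tenosynovitis described in the inclusion criteria".

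The plan then says "we plan to enroll 1000 patients total into this study", a figure reached "when combining all possible tenosynovitides encountered at Emory". On analysis: "Patients will be grouped together for analysis and also broken into subgroups for sub-analysis based on primary diagnosis for injection".

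The same section sets significance at P < .05 and lists an "unpaired, 2-tailed Student t test to compare means for normally distributed data". It also names the Mann-Whitney U test for the comparison of post-injection VAS, and it calls for 95% confidence intervals. Study Design describes random assignment to two groups without giving a ratio. No power is stated anywhere.

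**The concern.** A two-group calculation for a difference in means normally yields a number per group. Here the number carries no unit when it is derived, and it is then attached to patients with each tenosynovitis, which on a plain reading means both arms together. The two readings differ by a factor of two, and this is the only size the plan gives for a diagnosis.

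The figure matters because each diagnosis is to be analysed separately. Someone following the text could regard a diagnosis with 63 patients as adequately sized for a 1-point difference. At that size a true 1-point difference would be missed about half the time, and a non-significant result could be misread as showing that lidocaine makes no difference in that diagnosis.

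**Working it through.** **Inputs from the plan.** Difference 1 point and SD 2 (Statistical Analysis, sample-size paragraphs); two-sided 5% test (Statistical Analysis); two randomised groups (Study Design).

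**Assumptions not in the plan.** 80% power and 1:1 allocation.

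**Step 1: reproduce the 63.**

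n per arm = 2 × (1.960 + 0.842)² × 2² / 1² = 62.8, so 63 per arm and 2 × 63 = 126 per diagnosis.

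The plan's number is therefore reproduced exactly, as a per-arm figure. With 90% power the same formula gives 84.1, so 85 per arm; 80% is the conventional power that fits.

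**Step 2: could 63 be a two-arm total?** The totals required for both arms together are:

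- two-sided, 80% power: 126
- one-sided, 80% power: 100
- two-sided, 90% power: 170
- two-sided, 50% power: 62

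Of these, only 50% power comes near 63.

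**Step 3: what each reading delivers (SD 2, true difference 1 point).** SE = 2 × √(1/n₁ + 1/n₂). Power is from the noncentral t distribution with noncentrality 1/SE.

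| | 63 in total (31 v 32) | 63 per arm (63 v 63) |
|---|---|---|
| SE | 0.504 | 0.356 |
| Noncentrality | 1.98 | 2.81 |
| Critical t (df) | 2.000 (61) | 1.979 (124) |
| Power, t-test | 49.7% | 79.5% |
| Power, Mann-Whitney | about 48% | about 78% |
| Detectable at 80% power | about 1.4 points | about 1.0 point |
| 95% CI half-width | 2.000 × 0.504 = 1.01 | 1.979 × 0.356 = 0.71 |

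The Mann-Whitney row assumes normal data and multiplies the sample size by the test's relative efficiency of 0.955: 31.5 × 0.955 = 30.1 per arm and 63 × 0.955 = 60.2 per arm. The detectable difference is (1.960 + 0.842) × SE, that is 1.41 and 1.00.

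The 49.7% does not depend on the assumed 80%. It needs only the plan's difference, SD and significance level, with near-equal arms.

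**Step 4: pooled comparison.** With 500 v 500, SE = 2 × √(2/500) = 0.126 and 1/SE = 7.9. Power is over 99.9% for 1 point.

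**Step 5: does the total of 1000 settle the unit?** The Inclusion Criteria list 8 distinct sites if the repeated elbow is counted once and the small joints of the hand are taken together, or 10 if PIP, DIP and MP are counted separately.

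- Per-arm reading: 8 × 126 = 1008; 10 × 126 = 1260.
- In-total reading: 8 × 63 = 504; 10 × 63 = 630.

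The match of 1008 with 1000 favours the per-arm reading. It is not proof. The list is explicitly open-ended, no quotas are set, and the subgroups are defined by primary diagnosis, whereas the list is of sites; trigger finger and de Quervain tenosynovitis are diagnoses.

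**The case against.** The strongest reply is that this is only a missing unit. The calculation itself is correct. The source trial is described by its size in each group, the 63 is introduced as the number for comparing two groups, and 8 × 126 comes within 1% of the planned 1000. A statistician reading the paragraph would probably supply the words per arm. This stands as a judgement of likely intent. It does not remove the problem: the plan gives the unit for the source trial and omits it for its own target, and no other section supplies it. If per arm was meant, the sentence still needs correcting.

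The second reply is that the consequence is conditional and secondary. That also stands. The 63 is an aim and not a cap, nothing stops a diagnosis at 63, enrolment by diagnosis is unknown, and the plan does not say that a diagnosis with 63 patients will be reported as powered.

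A reader might go further and infer that the trial as a whole is underpowered. The documents do not support this, because patients are also analysed together and the pooled comparison has ample power for 1 point. Nor do they support an inference that the SD was taken wrongly from the source: an SD of 2 with 30 per group gives an SEM of 2/√30 = 0.365, which rounds to the quoted 0.4.

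**Conclusion.** Wrong as written. The plan's inputs lead to 63 per arm, 126 per diagnosis, and the target sentence gives 63 per diagnosis. If applied literally, power for 1 point in a diagnosis subgroup is about 50% instead of about 80%, and the 95% confidence interval is about ±1.0 point instead of about ±0.7, so its half-width is as large as the difference sought.

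The identification of 63 as a per-arm number rests on 80% power and 1:1 allocation, both assumed. The power figures rest on the plan's SD of 2 and near-equal arms. The finding is confined to the sub-analyses by diagnosis. It would be tempting to say that the plan commits itself to subgroups with 50% power; the text does not show that, since it may have meant per arm and it sets no limit at 63.

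**What to change.** The sponsor should confirm that 63 was meant per arm and state the power and allocation ratio used. If so, restate the target along these lines: *63 per arm (126 per diagnosis) for a 1-point difference, SD 2, about 80% power, two-sided 5%, 1:1 allocation*.

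Add two statements:

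- 126 is the size at which a diagnosis subgroup can be described as powered for 1 point. It is not an enrolment quota. The planned total stays at 1000, so some diagnoses may not reach it (1000/126 = 7.9, so at most seven could all do so).
- Any diagnosis with fewer than 63 per arm is reported as an estimate with its 95% confidence interval, which the plan already calls for, and is not described as powered for 1 point.

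The cost is a reworded paragraph and one reporting rule. No patients are added and the pooled analysis is unchanged. The downside is a less favourable stated sensitivity for the smaller diagnoses.

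### The target of 63 patients per tenosynovitis is not ensured by the enrolment plan, and 63 is a per-arm, trigger finger figure that 1000 patients can supply for at most seven diagnoses

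*Combined protocol and SAP*

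**What the plan says.** The Statistical Analysis section takes VAS-pain at the time of injection as the primary outcome for the power analysis. It uses a 1-point difference (4.5 against 3.5) and an SD of 2 from a published trial, reference 32, and concludes that "the number needed to treat to detect a difference between the treatment and placebo group would be 63". It then turns that number into a target by diagnosis: "Therefore, we aim for a sample size of 63 patients for each possible tenosynovitis described in the inclusion criteria". The overall size follows separately: "we plan to enroll 1000 patients total into this study". Patients are to be analysed together and also in subgroups by primary diagnosis.

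The Inclusion Criteria admit all willing adults injected for "Tenosynovitis of the upper extremity, including but not limited to, the shoulder, biceps, elbow, wrist, thumb, carpometacarpal, midcarpal, elbow, and small joints of the hand", with PIP, DIP and MP in brackets after the last item. Trigger finger has its own criterion below the list. De Quervain tenosynovitis is a separate aim in Background and Significance. The protocol gives no number of diagnoses, no minimum or maximum for any of them, no stratified randomisation and no expected case mix.

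The title of reference 32 shows a trial in trigger finger injection. The protocol describes it as "comparing needle-free jet lidocaine for pre-corticosteroid injection anesthesia with simultaneous lidocaine and corticosteroid injection".

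**The concern.** A sample size stated for each diagnosis implies that each diagnosis can support its own conclusion. For that to hold, the number must be the right one for a two-arm comparison within a diagnosis, the enrolment rules must produce it, and the assumptions behind it must apply at each site. The protocol secures none of the three. It does not say whether 63 is per arm or per diagnosis, enrolment by diagnosis is left to whoever attends clinic, and the only variability figure comes from trigger finger, although the Study Design section says that volume, needle size and insertion site differ by condition.

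What is at stake is the analysis by diagnosis. The Hypotheses section mostly predicts equivalent results, while the planned tests look for differences and no margin is given. A diagnosis subgroup that is too small will often give a non-significant result. A statement that each diagnosis was adequately sized would invite readers to take that result as support for equivalence.

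**Working it through.** **Inputs.** From the Statistical Analysis section: difference 1 point; SD 2; P < .05; two-sided, from "unpaired, 2-tailed Student t test to compare means for normally distributed data"; total 1000. Assumed because not stated: 80% power, 1:1 allocation, no dropout.

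**1. Reproducing 63.** For two means, n per arm = 2 × (1.960 + 0.842)² × SD² / difference² = 2 × 7.85 × 4 / 1 = 62.8, so 63 per arm and 126 for both arms. The t-based version gives 63.8, so 64 per arm. Other settings do not give 63: 85% power needs 72 per arm and 90% needs 85; a one-sided test at 80% needs 50 per arm (100 in all); a one-sample or paired t test needs 34. No variant tried gives 63 as a two-arm total.

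**2. If 63 is the total for a diagnosis.** That is 31.5 per arm. Standard error = 2 × √(2/31.5) = 0.504. Then 1/0.504 − 1.960 = 0.024, so power is about 51% (50% by t test).

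**3. Number of diagnoses named.** The list has 8 distinct sites if the small joints count as one (elbow appears twice), or 10 if PIP, DIP and MP are separate. Adding trigger finger and de Quervain as separate diagnoses gives up to 12. The wording leaves the list open beyond that.

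**4. What 1000 patients can cover.** At 63 each, 1000/63 = 15.9, so 15 diagnoses fit. At 126 each, 1000/126 = 7.9, so 7 fit.

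| Diagnoses | Needed at 63 each | Needed at 126 each | Patients each if spread evenly | Power for 1 point, even spread |
|---|---|---|---|---|
| 8 | 504 | 1008 | 125 | 80% |
| 10 | 630 | 1260 | 100 | 71% |
| 12 | 756 | 1512 | 83 | 63% |

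The last column uses power = Φ(1/SE − 1.960) with SE = 2 × √(2/n per arm). For 10 diagnoses, n = 50 per arm, SE = 0.400, and Φ(2.500 − 1.960) = Φ(0.540) = 71%.

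**5. Is 63 per diagnosis ensured?** A diagnosis needs 63/1000 = 6.3% of enrolments. If one diagnosis is commonest and the others are equal (an illustration, since no case mix is given), the others miss 63 once the commonest exceeds 1 − 9 × 0.063 = 43.3% with 10 diagnoses, or 1 − 11 × 0.063 = 30.7% with 12.

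**6. Sensitivity to the SD.** The SEM of 0.4 with 30 per group, quoted in the same sentence as the SD of 2, implies SD = 0.4 × √30 = 2.19. That needs 76 per arm (152 per diagnosis), so 1000 covers 6 diagnoses. Power is then 73% with 63 per arm and 44% with 63 in total.

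**7. Pooled comparison.** With 500 per arm, SE = 2 × √(2/500) = 0.126 and 1/0.126 − 1.960 is about 5.9, so power is above 99.9% under the plan's own assumptions.

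**The case against.** The strongest reply is that the target, read as written, fits. Twelve diagnoses at 63 need 756 patients, which leaves 244 spare. A reader might infer that the plan cannot deliver 63 per tenosynovitis within 1000. The documents do not support that: on this reading the target is only not ensured. It becomes unreachable for all the named diagnoses only on the per-arm reading. Even there, with the shortest count of 8, the gap is 8 patients (1008 against 1000) if enrolment is perfectly even.

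A reader might also infer that particular sites, such as midcarpal or DIP, will be rare and that common diagnoses will absorb the 1000. The protocol gives no frequencies by site and asserts high volume for all types, so this remains a possibility. Nor is there evidence that the SD is larger at other sites; the point is only that none is given for them. From the protocol's description one might infer that reference 32 had lidocaine in both arms and so gives no SD for steroid alone. That rests on one sentence about a paper that is not among the documents, and nothing here depends on it.

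Finally, the pooled analysis is planned and is amply sized, so the trial as a whole is not underpowered on this outcome. That stands and limits the point to conclusions by diagnosis. The reply does not explain why a figure that reproduces only per arm is used as a number of patients per diagnosis, nor what would make each diagnosis reach it.

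**Conclusion.** The concern holds for the analysis by diagnosis. Taken as a total, 63 per diagnosis is attainable but not ensured, and it gives about 50% power. Taken per arm, it gives about 80% power but needs 126 per diagnosis, which 1000 patients can supply for at most 7 diagnoses against the 8 to 12 named. On neither reading does the plan provide an adequate size for every listed tenosynovitis. The trigger finger basis is carried to the other sites without justification.

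This rests on an assumed 80% power, 1:1 allocation, no dropout and the plan's SD of 2; the SD of 2.19 implied by the quoted SEM makes the shortfall larger. The count of diagnoses depends on grouping. The documents do not say that a non-significant subgroup will be called equivalent; that is a risk to close off, not a stated intention. The point should be corrected, but it does not threaten the pooled result.

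**What to change.** In the Statistical Analysis section:

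- State that 63 is a per-arm figure derived from trigger finger, hence 126 per diagnosis, and give the power behind it. Withdraw the claim that every tenosynovitis will be adequately sized.
- Make the pooled comparison primary.
- Name in advance the few diagnoses for which a separate conclusion will be drawn if they reach 126 (63 in each arm).
- Report all other diagnoses as exploratory, with the estimate and 95% CI, and state that a non-significant result in them will not be read as equivalence.

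The cost is protocol wording and a running count by diagnosis. The total stays at 1000. Neither a closed list of sites nor enrolment caps are needed; both would be trade-offs against the broad eligibility, and neither settles whether 63 is per arm. The downside is that fewer diagnoses carry a formal conclusion.
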